#### Table 14.3.7.1 Summary of concomitant medications (Other than FIX replacement therapy) by therapeutic grouping - Full analysis set

ATC level 1 ATC level 2	Cohort 1 (N=x) n (%) E	Cohort 2 (N=x) n (%) E	Total (N=x) n (%) E	
Nasal Preparations	x (xxx) x	x (xxx) x	x (xxx) x	
Sensory Organs	x (xxx) x	x (xxx) x	x (xxx) x	
Ophthalmological And Otological Preparations	x (xxx) x	x (xxx) x	x (xxx) x	
Genito Urinary System And Sex Hormones	x (xxx) x	x (xxx) x	x (xxx) x	
Urologicals	x (xxx) x	x (xxx) x	x (xxx) x	
***** ATC1 not coded *****	x (xxx) x	x (xxx) x	x (xxx) x	
***** ATC2 not coded *****	x (xxx) x	x (xxx) x	x (xxx) x	
Antineoplastic And Immunomodulating Agents	x (xxx) x	x (xxx) x	x (xxx) x	
Antineoplastic Agents	x (xxx) x	x (xxx) x	x (xxx) x	

N: Number of patients in Full Analysis Set (FAS). ATC Class: Anatomical Therapeutic Chemical Classification.

n: Number of patients with the medication. (%): Percentage of patients with the medication in FAS. E: Number of Medications.

Cohort 1: AAV5-hFIX 5.0 x 10^12 gc/kg, Cohort 2: AAV5-hFIX 2.0 x 10^13 gc/kg

Medication coded with WHO DD version 143E

Sponsor: uniQure biopharma B.V	Date 27MAY2021		larix
Trial ID: CT-AMT-060-01	Table Challe		Final Version 05
Eudrac1 No: 2013-00557942-42	l adie Shelis		Page 64 01 66
Table 14.3.7.2 Summary of time	to first shedding negative (day	ys) - Vector DNA - Full analy	sis set
	Cohort 1 (N=x)	Cohort 2 (N=x)	Total (N=x)
Vector DNA Blood (copies/mL)			
n	x (xxx) x	x (xxx) x	x (xxx) x
Mean (SD)	x (xxx) x	x (xxx) x	x (xxx) x
Median	x (xxx) x	x (xxx) x	x (xxx) x
Min ; Max	x (xxx) x	x (xxx) x	x (xxx) x
Vector DNA Faeces (conjes/mg)			
n	x (xxx) x	v (vvv) v	v (vvv) v
Mean (SD)			
Median	x (xxx) x	x (xxx) x	X (XXX) X
Min - Mar	x (xxx) x	x (xxx) x	x (xxx) x
Min ; Max	x (xxx) x	x (xxx) x	x (xxx) x
Vector DNA Nasal Secretion (copies per s	wab)		
n	x (xxx) x	x (xxx) x	x (xxx) x
Mean (SD)	x (xxx) x	x (xxx) x	x (xxx) x
Median	x (xxx) x	x (xxx) x	x (xxx) x
Min ; Max	x (xxx) x	x (xxx) x	x (xxx) x
vector DNA Saliva (copies/mL)			
n Maan (SD)	x (xxx) x	x (xxx) x	x (xxx) x
Marcan (SD)	x (xxx) x	x (xxx) x	x (xxx) x
Median	x (xxx) x	x (xxx) x	x (xxx) x
Min ; Max	x (xxx) x	x (xxx) x	x (xxx) x

N: Number of patients in Full Analysis Set (FAS). n: Number of patients who have met the criterion for shedding negative.

First shedding negative is defined for a specific matrix when 3 consecutive negative samples have been detected for the patient for that particular type of matrix.

Cohort 1: AAV5-hFIX 5.0 x 10^12 gc/kg, Cohort 2: AAV5-hFIX 2.0 x 10^13 gc/kg

UniQure/AMT/CT-AMT-060-01/current - tab\_shed\_neg.sas/tab\_shed\_neg.rtf/10jan2018

Sponsor: uniQure biopharma B.V	Date 27MAY2021	larix
Trial ID: CT-AMT-060-01		Final Version 05
EudraCT No: 2013-00557942-42	Table Shells	Page 65 of 66

#### Table 14.3.7.2 Summary of time to first shedding negative (days) - Vector DNA - Full analysis set

	Cohort 1	Cohort 2	Total	
	(N=5)	(N=5)	(N=10)	
Vector DNA Semen (copies/m	L)			
n	x (xxx) x	x (xxx) x	x (xxx) x	
Mean (SD)	x (xxx) x	x (xxx) x	x (xxx) x	
Median	x (xxx) x	x (xxx) x	x (xxx) x	
Min ; Max	x (xxx) x	x (xxx) x	x (xxx) x	
Vector DNA Urine (copies/mL	.)			
n	x (xxx) x	x (xxx) x	x (xxx) x	
Mean (SD)	x (xxx) x	x (xxx) x	x (xxx) x	
Median	x (xxx) x	x (xxx) x	x (xxx) x	
Min ; Max	x (xxx) x	x (xxx) x	x (xxx) x	

N: Number of patients in Full Analysis Set (FAS). n: Number of patients who have met the criterion for shedding negative.

First shedding negative is defined for a specific matrix when 3 consecutive negative samples have been detected for the patient for that particular type of matrix.

Cohort 1: AAV5-hFIX 5.0 x 10^12 gc/kg, Cohort 2: AAV5-hFIX 2.0 x 10^13 gc/kg

UniQure/AMT/CT-AMT-060-01/current - tab\_shed\_neg.sas/tab\_shed\_neg.rtf/10jan2018

Sponsor: uniQure biopharma B.V	Date 27MAY2021	larix
Trial ID: CT-AMT-060-01 EudraCT No: 2013-00557942-42	Table Shells	Final Version 05 Page 66 of 66

### Figures to be generated – no shells

Figure 14.2.21 FIX activity over time - One Stage aPTT assay - Cohort 1 - Period: From tapering-off to cut-off - FAS Figure 14.2.22 FIX activity over time - One Stage aPTT assay - Cohort 2 - Period: From tapering-off to cut-off off - FAS

Figure 14.3.5.1 Individual profile plot of T-cell (AAV5-capsid) ELISPOT ((SFC)/million PBMCs) - Cohort 1 - Period: From IMP to cut-off - FAS Figure 14.3.5.2 Individual profile plot of T-cell (AAV5-capsid) ELISPOT ((SFC)/million PBMCs) - Cohort 2 - Period: From IMP to cut-off - FAS Figure 14.3.5.3 Individual profile plot of Vector DNA blood (copies/mL) - Cohort 1 - Period: From IMP to cut-off - FAS Figure 14.3.5.4 Individual profile plot of Vector DNA blood (copies/mL) - Cohort 2 - Period: From IMP to cut-off - FAS Figure 14.3.5.5 Individual profile plot of Vector DNA faeces (copies/mg) - Cohort 1 - Period: From IMP to cut-off - FAS Figure 14.3.5.6 Individual profile plot of Vector DNA faeces (copies/mg) - Cohort 2 - Period: From IMP to cut-off - FAS Figure 14.3.5.7 Individual profile plot of Vector DNA nasal (copies per swab) - Cohort 1 - Period: From IMP to cut-off - FAS Figure 14.3.5.8 Individual profile plot of Vector DNA nasal (copies per swab) - Cohort 2 - Period: From IMP to cut-off - FAS Figure 14.3.5.9 Individual profile plot of Vector DNA saliva (copies/mL) - Cohort 1 - Period: From IMP to cut-off-FAS Figure 14.3.5.10 Individual profile plot of Vector DNA saliva (copies/mL) - Cohort 2 - Period: From IMP to cut-off - FAS Figure 14.3.5.11 Individual profile plot of Vector DNA semen (copies/mL) - Cohort 1 - Period: From IMP to cut-off - FAS Figure 14.3.5.12 Individual profile plot of Vector DNA semen (copies/mL) - Cohort 2 - Period: From IMP to cut-off - FAS Figure 14.3.5.13 Individual profile plot of Vector DNA urine (copies/mL) - Cohort 1 - Period: From IMP to cut-off - FAS Figure 14.3.5.14 Individual profile plot of Vector DNA urine (copies/mL) - Cohort 2 - Period: From IMP to cut-off-FAS Figure 14.3.5.15 Chemistry: Individual profile plot of Albumin (g/L) - Cohort 1 - Period: From IMP to cut-off - FAS Figure 14.3.5.16 Chemistry: Individual profile plot of Albumin (g/L) - Cohort 2 - Period: From IMP to cut-off - FAS Figure 14.3.5.17 Chemistry: Individual profile plot of Alanine Aminotransferase (U/L) - Cohort 1 - Period: From IMP to cut-off - FAS Figure 14.3.5.18 Chemistry: Individual profile plot of Alanine Aminotransferase (U/L) - Cohort 2 - Period: From IMP to cut-off - FAS Figure 14.3.5.19 Chemistry: Individual profile plot of Aspartate Aminotransferase (U/L) - Cohort 1 - Period: From IMP to cut-off - FAS Figure 14.3.5.20 Chemistry: Individual profile plot of Aspartate Aminotransferase (U/L) - Cohort 2 - Period: From IMP to cut-off - FAS Figure 14.3.5.21 Chemistry: Individual profile plot of Bilirubin (umol/L) - Cohort 1 - Period: From IMP to cut-off - FAS Figure 14.3.5.22 Chemistry: Individual profile plot of Bilirubin (umol/L) - Cohort 2 - Period: From IMP to cut-off - FAS Figure 14.3.5.23 Chemistry: Individual profile plot of C Reactive Protein (nmol/L) - Cohort 1 - Period: From IMP to cut-off - FAS Figure 14.3.5.24 Chemistry: Individual profile plot of C Reactive Protein (nmol/L) - Cohort 2 - Period: From IMP to cut-off - FAS Figure 14.3.5.25 Chemistry: Individual profile plot of Gamma Glutamyl Transferase (U/L) - Cohort 1 - Period: From IMP to cut-off - FAS Figure 14.3.5.26 Chemistry: Individual profile plot of Gamma Glutamyl Transferase (U/L) - Cohort 2 - Period: From IMP to cut-off - FAS Figure 14.3.6.1 Vital Signs: Individual profile plot of Systolic Blood Pressure (mmHg) - Cohort 1 - Period: From IMP to cut-off - FAS Figure 14.3.6.2 Vital Signs: Individual profile plot of Systolic Blood Pressure (mmHg) - Cohort 2 - Period: From IMP to cut-off - FAS Figure 14.3.6.3 Vital Signs: Individual profile plot of Diastolic Blood Pressure (mmHg) - Cohort 1 - Period: From IMP to cut-off - FAS Figure 14.3.6.4 Vital Signs: Individual profile plot of Diastolic Blood Pressure (mmHg) - Cohort 2 - Period: From IMP to cut-off - FAS Figure 14.3.6.5 Vital Signs: Individual profile plot of Pulse Rate (beats/min) - Cohort 1 - Period: From IMP to cut-off - FAS Figure 14.3.6.6 Vital Signs: Individual profile plot of Pulse Rate (beats/min) - Cohort 2 - Period: From IMP to cut-off - FAS

Figure 14.3.6.7 Vital Signs: Individual profile plot of Temperature (°C) - Cohort 1 - Period: From IMP to cut-off - FAS

Figure 14.3.6.8 Vital Signs: Individual profile plot of Temperature (°C) - Cohort 2 - Period: From IMP to cut-off - FAS

Sponsor: uniQure biopharma B.V

Date 27MAY2021

Trial ID: CT-AMT-060-01 EudraCT No: 2013-00557942-42

Listing Shells

## 16.2.2 Protocol deviations
### CSL Behring LLC AMT-060 Protocol No: CT-AMT-060-01

Sponsor: uniQure biopharma B.V

Date 27MAY2021

Listing Shells

Listing 16.2.2.1 Protocol deviations

NO DATA FOUND FOR THIS LISTING

 $UniQure/AMT/CT\text{-}AMT\text{-}060\text{-}01/current\text{-}lst\_emptylist.sas/lst\_prodev.rtf/ddmmmyyyy$ 

CSL Behring LLC AMT-060 Protocol No: CT-AMT-060-01

Sponsor: uniQure biopharma B.V	Date 27MAY2021	larix
Trial ID: CT-AMT-060-01 EudraCT No: 2013-00557942-42	Listing Shells	Final Version 05 Page 12 of 92

### List of Abbreviations

Definition
American Association for the Study of Liver Diseases
Adeno-Associated Viral vector serotype 5
Adverse Event
Alanine Aminotransferace
A spartate A minotransferase
complementary Deoxyribonucleic Acid
Clinical Trial Protocol
Data Monitoring Committee
Factor IX
Independent Ethics Committee
Investigational Medical Product
Institutional Daview Decad
Serious Adverse Event

## List of Terms

Term	Definition
AAV5-hFIX	Adeno-associated viral vector containing a codon-optimized human factor IX gene

uniQure biopharma B.V. Proprietary and Confidential Final version 1.0, 30 December 2014 Page 3 of 14 Trial ID: CT-AMT-060-01

Data Monitoring Committee Charter

uniQure

## uniQure

## 3. Purpose

The Data Monitoring Committee (DMC) is a committee established by uniQure, composed of individuals with appropriate and relevant experience to assess safety data of subjects participating in the clinical trial, CT-AMT-060-01.

The purpose of this charter is to define how the DMC will operate prior to and during the conduct of the clinical trial, CT-AMT-060-01.

## 4. Trial Design

Trial CT-AMT-060-01 has an open-label, uncontrolled, single-dose, dose-ascending design and consists of two cohorts. The trial will be conducted at multiple centres in multiple countries in male patients, aged  $\geq 18$  years, with severe haemophilia B or moderately severe haemophilia B with a severe bleeding phenotype defined as:

- Known coagulation Factor IX (FIX) deficiency with plasma FIX activity level
   < 1% (severe) or plasma FIX activity level ≥ 1% and ≤ 2% (moderately severe) and

- currently on prophylactic FIX replacement therapy for a history of bleeding, or
- currently on on-demand therapy with a current or past history of frequent bleeding (defined as four or more bleeding episodes in the last 12 months or chronic haemophilic arthropathy [pain, joint destruction, and loss of range of motion] in one or more joints).

Patients should have had more than 150 previous exposure days of treatment with FIX protein.

The Investigational Medicinal Product (IMP) is a recombinant adeno-associated viral vector of serotype 5 (AAV5) containing the codon-optimized hFIX complementary Deoxyribonucleic Acid (cDNA) under the control of a liver-specific promoter. The IMP is identified as AAV5-hFIX. The pharmaceutical form of AAV5-hFIX is solution for intravenous infusion.

Subjects will be allocated to one of two cohorts with the following planned dose levels: - Cohort 1 (5 subjects): AAV5-hFIX  $5.0 \times 10^{12}$  gc/kg - Cohort 2 (5 subjects): AAV5-hFIX  $2.0 \times 10^{13}$  gc/kg

Subjects will receive the IMP on only one occasion and will thereafter be followed for five years with respect to safety and with respect to efficacy measured as levels of FIX, bleeding patterns and consumption of FIX replacement therapy.

## 5. Responsibilities and Tasks of the DMC

The primary responsibilities of the DMC are to:

uniQure biopharma B.V. Proprietary and Confidential Final version 1.0, 30 December 2014 Page 6 of 14

Trial ID: CT-AMT-060-01

- periodically review and evaluate accumulated safety data from trial CT-AMT-060-01 throughout the entire trial period, and
- identify potential safety signals, and
- make recommendations to uniQure concerning trial continuation, protocol modifications, additional analyses or trial suspension based on available safety data

The DMC chair will:

- Chair the DMC meetings
- Ensure written statements/recommendations and minutes are approved and stored
- Request additional data and/or analysis and/or ad hoc experts to be called for

The DMC member acting as independent external statistician will:

- Prepare data packages to the DMC and Sponsor
- Provide data package via secure website to DMC
- Assist the DMC in evaluating data and serve as interface with sponsor to if additional data or analyses are required.
- Be member of the DMC.
- Ensure that Sponsor provide presentation at open sessions for trial developments, as needed.
- Arrange DMC meetings
- Arrange meetings between Sponsor and DMC if the DMC provides a recommendation which different from "dosing and trial design should continue as planned" (see Section 6.2.4)

All DMC members (excluding the external independent statistician) will:

- evaluate available safety data from the first subject in each cohort prior to allowing dosing of the second subject in that particular cohort (see Section 5.1.2)
- evaluate available safety data from the second subject in each cohort prior to allowing dosing of the subsequent 3 subjects in that particular cohort (see Section 5.1.2)
- evaluate available safety data from subjects in Cohort 1 prior to allowing dosing of subjects in Cohort 2 (see Section 5.1.3)

These evaluations will take place at Gateway Meetings (see Section 6.3).

In relation to these evaluations, the DMC will adhere to Trial Stopping Rules (see Section 5.1.1).

To strengthen its evaluations, the DMC may recommend specific interim analyses to be performed during the course of the trial.

uniQure biopharma B.V. Proprietary and Confidential Final version 1.0, 30 December 2014 Page 7 of 14

Trial ID: CT-AMT-060-01

## uniQure

### 5.1 Trial Stopping Rules and Decisions on dosing next Subject(s)

### 5.1.1 Trial Stopping Rules

As the trial is a one-dose trial, stopping rules are relevant only for the recruitment period. Independently of any changes to the recruitment, subjects who have already been dosed will be followed as per protocol to the end of trial.

The following events will lead to decision to pause dosing, i.e. stop subject recruitment to allow for evaluation and assessment of the implications of the event for further subject dosing:

- 1. A more than fivefold increase in ALT, AST or both in one or more subjects after IMP administration which is not manageable by steroid rescue treatment implemented according to AASLD guidelines (see clinical trial protocol for CT-AMT-060-01).
- 2. An SAE judged as probably or possibly related to the IMP and which pose either an immediate risks to subject's health or is likely to adversely affect the subject's health long term. This includes events classified as adverse events qualifying for special as listed in the clinical trial protocol, if these are judged as probably or possibly related to the IMP. The development of an inhibitor towards FIX in one subject is not a cause for stop of subject recruitment, however the development of an FIX inhibitor in more than one subject should lead to pausing of dosing and further investigations of causal relationship
- 3. Death of a subject, after having received the IMP, that is judged as related to the IMP
- 4. The occurrence of a malignancy at any point after gene transfer that is judged as probably or possibly related to the IMP.

### 5.1.2 Decision to dose the next Subject(s) within a Cohort

The DMC will evaluate the available safety data collected during a period of minimum 24 hours after IMP administration to the 1st subject in a cohort and recommend if and when dosing of the 2nd subject in the cohort can be initiated. Similarly, after the 2nd subject has been dosed in a cohort, the DMC will evaluate available safety data collected during a period of minimum 24 hours after IMP administration to this second subject and recommend if and when dosing of the subsequent 3 subjects in the cohort can be initiated.

### 5.1.3 Decision to start Cohort 2

The DMC will evaluate all available safety data collected during the period of a minimum of 12 weeks after IMP administration in the first 3 subjects of Cohort 1 and for a minimum of 4 weeks after IMP administration in subjects 4 and 5 of Cohort 1.

If none of the events listed in Section 5.1.1 have occurred, the DMC may recommend to initiate Cohort 2. If one or more of these events have occurred, the DMC may recommend

uniQure biopharma B.V. Proprietary and Confidential Final version 1.0, 30 December 2014 Page 8 of 14

CSR Version: Final Date: 06 January 2022

Trial ID: CT-AMT-060-01

dosing to be paused while the event(s) is/are further investigated including the implications for further dosing and dose level.

## 6. DMC Meetings

#### 6.1 Kick-off Meeting

A kick-off meeting will be held before screening of the first subject. During this meeting the following will be presented and discussed:

- Background information and mechanism of action of AAV5-hFIX
- The presently known safety profile of AAV5-hFIX
- Clinical Trial Protocol (CTP) and CTP amendments, if any

The kick-off meeting must be attended by all DMC members and by representatives of uniQure. Sponsor's Drug Safety Expert (DSE), or delegate, will send, in a timely manner, all documents necessary to prepare for this meeting to all participants.

The purpose of the kick-off meeting is to:

- Review, discuss and approve the DMC Charter, including the role and responsibilities of the DMC. The DMC members may in the context of this discussion propose changes to the DMC Charter; however, uniQure is responsible for final decisions relating to the charter
- Review, discuss and train on the IMP and CTP, and associated documents (e.g. patient information sheets, the IB, comments from Independent Ethics Committee(s) (IECs)/ Institutional Review Board(s) (IRBs), reviews, relevant literature, and other research-related document(s))
- Establish the frequency of the DMC meetings, including decisions related to the organization of the meeting (e.g. face-to-face meetings, teleconferences)
- Pre-book date and time for next meeting to be held.
- Review guidelines for assessing the clinical trial progress and safety data, the clinical trial modification and/or termination guidelines, and if applicable, for efficacy based on plans specified in the CTP.
- Develop procedures for conducting business (e.g. voting rules, attendance).

Sponsor's DSE, or delegate, will prepare the minutes, as applicable, of this kick-off meeting and ensure distribution of these, as relevant.

Sponsor's responsible chief medical officer, or delegate, will ensure finalization of the DMC Charter and the approval of this by sponsor's responsible chief medical officer and the DMC Chair. The DMC Chair approves the DMC Charter on behalf of the DMC. The DMC Charter must be approved prior to start of screening of subjects. Once the approved DMC Charter is accepted by all DMC members by signature, the DMC will be considered activated.

uniQure biopharma B.V. Proprietary and Confidential Final version 1.0, 30 December 2014 Page 9 of 14

Trial ID: CT-AMT-060-01

### 6.2 Periodic DMC Meetings

The DMC will meet at periodic intervals to review cumulative safety data. The DMC meetings will take form as

- Gateway meetings (see Section 6.3)
- Bi-annual meetings (see Section 6.4)
- Other meetings (see Section 6.5)

For all meetings, the principles regarding meeting preparation, format of meetings, minutes of meetings and DMC recommendations, described in Sections 6.2.1 - 6.2.4, will be followed.

#### 6.2.1 Preparation of Periodic DMC Meetings

The external independent statistician will prepare a data package with all relevant safety data available and distribute this among DMC members and sponsor representatives. The agenda for each meeting will include:

- Review of data available
- Discussion of the need for additional data
- Decision of DMC recommendation

#### 6.2.2 Format of Meetings

Each DMC meeting following the kick-off meeting will, as necessary, be divided into two sessions: An open session and a closed session (both typically held as teleconferences). At least 3 members of the DMC, including the DMC Chair, must be participating in the closed session in order to have quorum.

#### Open Sessions

During open sessions, the DMC may request the attendance of sponsor's DSE, sponsor's responsible chief medical officer, investigator(s) and/or representatives of uniQure's clinical trial team, and/or independent consultant(s) to provide specific clarification or to respond to issues that have arisen. The open session should focus on the conduct and progress of the trial with special attention to safety and efficacy data. Data presented in the open session may include enrolment data, individual adverse event data and data on baseline characteristics.

#### Closed Sessions

During the closed sessions hosted by the external independent statistician, only DMC members must be present. During the closed sessions, the DMC must decide what recommendation(s) it will present to uniQure.

#### 6.2.3 Meeting Minutes

Minutes from the open sessions are prepared by the external independent statistician and approved by the DMC Chair. Minutes from the closed sessions are prepared by the DMC Chair assisted by the external independent statistician.

uniQure biopharma B.V. Proprietary and Confidential Final version 1.0, 30 December 2014 Page 10 of 14

Trial ID: CT-AMT-060-01

## uniQure

It is the goal that draft meeting minutes of open and closed sessions are prepared within 2 working days after the meeting. Draft meeting minutes are forwarded to all DMC members for their review, enabling final approved minutes within 7 calendar days after the meeting. Minutes of open and closed sessions are approved by the DMC Chair.

#### 6.2.4 DMC Recommendation(s)

DMC recommendations (regarding trial continuation, protocol modifications, additional analyses, or trial to be terminated) will be communicated to sponsor's DSE and sponsor's responsible chief medical officer. The recommendation(s) provided by the DMC to uniQure should be in writing and provided to uniQure immediately after the finalization of DMC meeting minutes. The recommendation and the related documentation should be filed in the Trial Master File (TMF).

The recommendation should include a brief ticking:

- a) No change recommended dosing and trial design should continue as planned
- b) Stopping or adjusting dose and/or trial design
- c) Stopping the trial immediately
- d) Putting the trial on hold while investigating issue

Furthermore, if recommendation b), c) or d) is ticked, a detailed explanation of this recommendation should be given. Additionally, a meeting should be set up between the DMC and Sponsor (arranged by the DMC member acting as external independent statistician).

uniQure's decision(s) to follow DMC recommendations will be documented in writing, signed by uniQure's DSE and Sponsor's responsible chief medical officer, and will be communicated by uniQure to:

- Investigator(s)
- IEC(s)/IRB(s)
- Competent authorities(s).

The communication to investigators, IEC(s)/IRB(s) and competent authorities will be organized by Sponsor's Clinical Trial Manager.

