administration to this second subject. The data monitoring committee will recommend if and when dosing of the subsequent 3 subjects can be initiated

- The dosing of the 3rd, 4th and 5th, and possibly 6th and 7th subject within a cohort must be separated by a minimum of 24 hours to ensure observation of any acute reactions.

Details on an adequate information communication system with and between the sites to ensure the timings of subject dosing within a cohort are adhered to will be described in the Trial Procedures Manual.

Figure 10-2, Intra-cohort Staggering Interval

After IMP administration, subjects will remain at the clinical trial site for 24 hours for monitoring of tolerance to IMP and for detection of potential immediate AEs. Hereafter, subjects will be followed with respect to safety and efficacy parameters for 5 years (260 weeks):

- Twice weekly up to week 12
- Every 2nd week from weeks 12 to 26
- Every 13th week from weeks 26 to 156 (6 months to 3 years)
- Every 26th week from weeks 156 to 260 (3 years to 5 years).

Subjects on prophylactic FIX replacement therapy will be tapered of their prophylactic FIX replacement therapy in the period from Visit 8 to Visit 14 (weeks 6-12). If the Investigator determines that FIX replacement therapy should be re-initiated, based on FIX levels or for other reasons, prophylactic FIX replacement therapy may be tapered again at a later time point. In relation to the withholding of FIX replacement therapy, additional visits may be required for the purpose of additional monitoring of FIX activity levels (see [Table 5-2](#)). For further details, please see [Section 11.4](#).

During the entire trial period, blood samples will be drawn regularly for measurements of FIX activity and FIX protein concentration in plasma. For subjects on prophylactic FIX replacement therapy, attempts should be made to allow blood sampling at time points where FIX activity and FIX protein concentration are expected to be at lowest justifiable levels. For further information, please see [Section 12.1.1](#).

Clinical Trial Protocol

Trial ID: CT-AMT-060-01

uniQure

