### 6.5 Other Meetings

The DMC members, if considered relevant, may call for additional telephone conferences or face-to-face meetings at any time.

Ad hoc specialists can be invited to DMC meetings as recommended by the DMC or uniQure.

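### The DMC Charter releases a stop or hold recommendation only after the minutes are final (goal 7 days), while the later subjects of a cohort may be dosed 24 hours apart

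*SAP*

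**What the plan says.** The DMC Charter (version 1.0, 30 December 2014) is filed with the SAP under 16.1.9.2.

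- **Release of recommendations (Charter 6.2.4).** Recommendations go to the sponsor's drug safety expert and chief medical officer. They are to be in writing and "provided to uniQure immediately after the finalization of DMC meeting minutes". The tick list has four options: (a) no change, (b) stopping or adjusting dose or design, "c) Stopping the trial immediately" and "d) Putting the trial on hold while investigating issue". All four share this one release rule.
- **Minutes (Charter 6.2.3).** "It is the goal that draft meeting minutes of open and closed sessions are prepared within 2 working days after the meeting". Review by all members follows, "enabling final approved minutes within 7 calendar days after the meeting".
- **Scope (Charter 6.2 and 6.5).** "For all meetings, the principles regarding meeting preparation, format of meetings, minutes of meetings and DMC recommendations" apply to gateway, bi-annual and other meetings alike. The last group includes ad hoc calls: under 6.5, members "may call for additional telephone conferences or face-to-face meetings at any time". No separate reporting route is given for these.
- **Who is present (Charter 6.2.2).** The recommendation is decided in a closed session without the sponsor.
- **Dosing (Charter 5.1.2 and Table 6-1; Protocol 9.1 and 10.1).** The last gateway meeting within a cohort follows subject 2 and releases the subjects after that together. Protocol 10.1 then says of the third, fourth, fifth and possibly sixth and seventh that each "subject within a cohort must be separated by a minimum of 24 hours to ensure observation of any acute reactions". Subjects 6 and 7 can occur only in Cohort 2 (Protocol 9.1).

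**The concern.** Two clocks run side by side and do not match. Protocol 19.2.1 gives the purpose of the 24-hour interval: to let acute, unexpected, related events and relevant CRP changes be assessed before the next subject is dosed. If the DMC meets on such an event and concludes that dosing should stop or pause, the written route for that conclusion is tied to minutes targeted for 7 days. A recommendation to stop at once travels by the same route as one to carry on.

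Protocol 13.4 is quicker elsewhere. Investigator follow-up information that may bear on other subjects' safety is due within 24 hours.

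Protocol 10.1 describes a first-in-man trial of a high-risk product, and Protocol 10.1.1 calls the product irreversible. What is at stake is that a subject could receive the single infusion after the independent committee had already decided against further dosing, but before the sponsor was due to be told.

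**Working it through.** **Inputs**

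- Minimum interval between doses from subject 3 on: 24 hours (Protocol 10.1 and 19.2.1).
- Cohort size: 5, or 7 for Cohort 2 with both optional subjects (Protocol 9.1).
- Release of the recommendation: on final minutes, goal 7 calendar days (Charter 6.2.3 and 6.2.4).
- Assumption, not in the documents: the ad hoc meeting takes place 12 hours after the dose of the subject whose event triggers it.

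**Duration of the dosing run.** With subject 3 at day 0, subject s is dosed at day s − 3. Subjects 3 to 5 take 5 − 3 = 2 days, and subjects 3 to 7 take 7 − 3 = 4 days. Both are shorter than 7 days.

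**Subjects dosed before notice is due.** If subject k triggers the meeting, it falls at m = (k − 3) + 0.5 days. With a lag of L days to notice, the exposed subjects are those with m < s − 3 < m + L. For k = 3 and L = 7 the window is day 0.5 to day 7.5. Subjects 4, 5, 6 and 7 are dosed on days 1, 2, 3 and 4, all inside it.

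| Trigger | Cohort size | L = 0 | L = 1 | L = 2 | L = 4 | L = 7 |
|---|---|---|---|---|---|---|
| Subject 3 | 5 | 0 | 1 | 2 | 2 | 2 |
| Subject 3 | 7 | 0 | 1 | 2 | 4 | 4 |
| Subject 4 | 5 | 0 | 1 | 1 | 1 | 1 |
| Subject 4 | 7 | 0 | 1 | 2 | 3 | 3 |
| Subject 5 | 5 | 0 | 0 | 0 | 0 | 0 |
| Subject 5 | 7 | 0 | 1 | 2 | 2 | 2 |

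The L = 7 column is the Charter's goal. The L = 2 column is not a release point, because draft minutes do not release the recommendation. L = 0 is notice at the close of the meeting.

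**Sensitivity to spacing.** The 24 hours is a floor. At d days between doses, with subject 3 as trigger and L = 7, subject s is exposed if 0.5 < (s − 3)d < 7.5.

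- d = 2: subjects 4 to 6 fall on days 2, 4 and 6 (inside), subject 7 on day 8 (outside). That is 2 in a cohort of 5, or 3 in a cohort of 7.
- d = 3: subjects 4 and 5 fall on days 3 and 6 (inside), subject 6 on day 9 (outside). That is 2 in either cohort.
- d = 7: subject 4 only, so 1.
- d above 7.5: none.

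**The case against.** The case against a serious problem has four parts.

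**Other routes to a pause exist.** The sponsor receives SAEs and special-notification events within 24 hours (Protocol 13.4). The latter include allergic reactions, thromboembolic events and transaminase rises above 1.5 times baseline (Protocol 13.6). The sponsor can end the trial itself (Protocol 19.2) and receives the DMC data package (Charter 6.2.1). Charter 5.1.1 says the listed events lead to a decision to pause, without mention of minutes, although Protocol 19.2.1 makes that pause optional. Investigators may act on an immediate hazard without prior ethics approval (Protocol 19.1). All of this stands. A reader might infer that the stopping rules cannot protect the later subjects at all. The documents do not support that, because the rules do not work through DMC minutes alone. But none of these routes brings the DMC's own conclusion to the sponsor sooner.

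**The Charter is less rigid than it looks.** Seven days is a goal, and nothing forbids finalising minutes the same day. The sentence naming the two sponsor recipients carries no time limit. Options (b) to (d) call for a DMC–sponsor meeting, and business procedures were left to the kick-off meeting (Charter 6.1). This stands in part. That meeting has no deadline, and because 7 days is only a goal, the delay may also be longer. The sponsor's signed decision and its notice to investigators have no deadline either.

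**Consecutive-day dosing is a worst case.** Patients are rare and spread over several countries (Protocol 10.1), and time is needed for shipment and preparation (Protocol 5). This stands: the counts are maxima at the permitted minimum.

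**There may be further DMC reviews.** Protocol 19.2.1 opens by saying the DMC reviews data before dosing and advises on the next subject. Its detail, however, covers only the reviews after subjects 1 and 2. Charter Table 6-1 likewise lists no gateway meeting within a cohort after subject 2.

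**Conclusion.** The point holds in a narrow form. The Charter's release rule, followed as written, can be slower than the whole run of doses left in a cohort, and it has no exception for a stop or hold. Decisions at gateway meetings are not exposed, because dosing waits for them. The gap is confined to ad hoc recommendations made after a cohort's second gateway meeting.

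After an event in subject 3, up to 2 further subjects (cohort of 5) or 4 (Cohort 2 enlarged to 7) could be dosed before notice is due. This rests on 24-hour spacing, a meeting 12 hours after the triggering dose, the 7-day goal being used in full, and no earlier action by the sponsor or investigators.

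A reader might infer 3 of 5 or 5 of 7, that is, everyone after subject 2 (5 − 2 = 3; 7 − 2 = 5). Those counts arise only if a late event in subject 1 or 2 triggers the meeting after the second gateway meeting but before subject 3 is dosed.

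Nor is this a live exposure. SAP section 5 required every enrolled patient to have reached Visit 14 for the first interim analysis, with a cut-off of 05AUG2016, so dosing appears complete. It is a low-cost defect of the plan as written and affects no subject still to be dosed.

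**What to change.** Reconcile Charter 6.2.3 and 6.2.4 with the 24-hour dosing interval by separating notice from minutes. For any recommendation other than option (a), the DMC sends the sponsor's drug safety expert and chief medical officer a brief written notice at the close of the closed session. Minutes and the detailed explanation follow on the existing 2-working-day and 7-calendar-day targets. State that this covers ad hoc meetings under 6.5.

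The change concerns only when a decision already taken is passed on. Stopping criteria, doses and dosing intervals stay unchanged. In the table under the minimum-spacing assumptions, it moves every row from the L = 7 column to L = 0, where no subject is dosed between meeting and notice.

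The cost is a wording change in the Charter and one short message per non-routine recommendation. With dosing apparently over, its practical use is for DMC output during the remaining follow-up and as wording for later charters.
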